**ABBREVIATIONS**

1-HOP	1-hydroxy naphthaline
AJCC	American Joint Committee on Cancer
BMI	body mass index
CI	confidence interval
CO	carbon monoxide
CPSR	Clinical Pharmacology Shared Resource of NCCC
CTP	Center for Tobacco Products at FDA
DHMC	Dartmouth-Hitchcock Medical Center
DNA	deoxyribonucleic acid
DSMAC	Data Safety Monitoring and Accrual Committee of NCCC
ENDD	electronic nicotine delivery device
FDA	Food and Drug Administration (U.S.)
FEV1	Forced Expiratory Volume in the first second
FVC	forced vital capacity
g	gram
HPLC	high performance liquid chromatography
mg	milligram
mL	milliliter
NCCC	Norris Cotton Cancer Center
NF- $\kappa$ B	nuclear factor-kappa B
Ng	nanogram
NNAL	4-(methylnitrosamino)-1-(3-pyridyl)-1-butanol
NNK	nicotine-derived nitrosamine ketone
NNN	N'-nitrosonornicotine
pmol	picomoles
ppm	parts per million
SPLC	second primary lung cancer
TLFB	Timeline Follow-Back Questionnaire
TSNA	tobacco-specific nitrosamine
US	United States

## ABSTRACT

Smoking causes many cancers but also affects survival and quality of life. Currently, the only option available to smokers who present with cancer is to quit, a notoriously difficult undertaking. E-cigarettes represent a modified-risk tobacco product that could reduce toxicity and improve medical outcomes. We test the appeal of e-cigarettes in cancer patients that smoke, and the impact of their use on excretion of smoke-related toxic metabolites. This pilot study tests the feasibility of a larger randomized trial to examine the effect of e-cigarette use, on measures of smoke-related toxicity and medical outcomes.

We will test feasibility in 40 smokers with aerodigestive tract cancers or bladder cancer, recruited over the course of nine months. In this 12 week single-arm study, smokers will be recruited from oncology and surgical clinics that treat these cancers, supplied with a current generation e- cigarette product and will return to clinic every 3 weeks for assessments on their e-cigarette and cigarette use along with markers for toxicity from tobacco smoke inhalation.

The overarching aim of the study is to determine the appeal of e-cigarettes as measured by the degree to which smokers with cancer adopt their use over the 9 weeks they are supplied with product. We will measure past use of e-cigarettes and cigarettes at baseline, 3, 6, 9, and 12 weeks. We will also assess the effect of e-cigarette substitution on toxicity by measuring expired carbon monoxide and urine NNAL, a carcinogenic metabolite of cigarette smoke. This translational research involves a multi-disciplinary team of prevention scientists, tobacco-use experts, statisticians, cancer clinicians, and psychiatrists and uses NCCC and White River Junction VAMC statistical and clinical trials resources.

## SPECIFIC AIMS AND HYPOTHESES

**Aim 1:** To evaluate the behavioral and psychological appeal of e-cigarettes among 40 chronic smokers with smoking-related cancers.

**Hypothesis 1 (H1):** Greater than 50% of study participants will report daily e-cigarette use at each assessment during the 9 weeks that e-cigs are provided, and mean satisfaction with e- cigarettes will be >4 on a 5-point scale. In a parallel process growth model for e-cigarette and cigarette use, there will be a significant negative correlation of growth slopes.

**Aim 2:** To evaluate the effect of e-cigarettes on biological markers of combusted tobacco toxicity.

**Hypothesis 2 (H2):** After 9 weeks, mean expired breath CO2 and urine NNAL will be reduced.

### Primary outcomes:

**Appeal (H1)**—E-cigarette use and amount of e-cigarette product used per week, proportion of participants that report e-cigarette use at each assessment, satisfaction scores for e-cigarettes, and whether they continue e-cigarette use at 12 weeks (3w after end of trial). Correlation between change in e-cigarette use and change in cigarette use.

Combustible Tobacco Toxicity (H2)—Exhaled CO, urine NNAL and 1-hydroxy naphthaline (1- HOP). Because smokers are good at regulating nicotine intake, we expect no change in urine cotinine over time.

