Reviews of studies have found that this approach does not reduce the chances that a smoker will quit smoking. Moreover, smoker titrate their nicotine intake when given multiple nicotine products, such that urine cotinine levels remain the same when smokers are given a nicotine replacement product. More recent unpublished data show that introduction of e-cigarettes in smokers does not result in rises in saliva cotinine, but is associated with changes in cigarette consumption.

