**Toxicity Assessment:** Our measures of toxicity, urine NNAL, 1-HOP and CO2 will be compared between the baseline and 9-week assessments via paired t-test. For NNAL, assuming a standard deviation of change in this measure of 3.8 pmol/mg creatinine (as was seen in Joseph et al. 2008), with 40 participants, this test will have 80% power at the two-sided 0.05 significance level to detect a change from baseline of 1.7 pmol/mg creatinine. There is not enough information available on 1-HOP to perform a test of power, so analysis of this metabolite is considered exploratory. For expired CO, assuming a standard deviation of change in this measure of 17.0 ppm, with 40 participants, a paired t-test comparing baseline to 9-week will have 80% power at the two-sided 0.05 significance level to detect a change from baseline that is 7.7 ppm. Additionally, since CO2 will be measured several times throughout the treatment period, the trajectory of change over time in this measure will be modeled via linear mixed effects models including random intercept and slope terms to account for repeated observations within individual. With repeated measurements of CO, the power for the mixed model will be greater than that of the paired t-test of change from baseline to detect this change over time.

We will also evaluate toxicity by analyzing cotinine level to assure that the adverse effect of increased cotinine (resultant from increased e-cigarette usage without similar decrease in combustible cigarettes). To do this, we will compute the number of participants with an increase in cotinine over the course of the study and consider this an adverse event. With 40 participants, confidence intervals around this adverse event percentage will be at most 0.32 percentage points. The table below gives the probability of observing at least 1 participant with an increase in cotinine given different true percentage of participants with this adverse event. For example, if the population-wide true percentage of participants with cotinine increase is 0.5%, then the probability of observing at least 1 of the 40 study participants with an increase is 0.18.

True percentage of participants with increase cotinine	Probability of observing at least 1 adverse event (increase in cotinine)
0.5%	0.18
1%	0.33
2%	0.55
5%	0.87
10%	0.99

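### Urine cotinine is expected not to change, but the only planned cotinine analysis counts participants with a rise, which tests that expectation poorly and is an inefficient way to see a fall

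*Combined protocol and SAP*

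**What the plan says.** The Primary outcomes section names exhaled CO, NNAL and 1-HOP as the toxicity outcomes for H2 and then adds: "Because smokers are good at regulating nicotine intake, we expect no change in urine cotinine over time". The background section on smoking as a cause of cancer gives the reason: smokers titrate their intake, "such that urine cotinine levels remain the same when smokers are given a nicotine replacement product". H2 itself covers only breath CO (printed as CO2) and urine NNAL.

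In the Toxicity Assessment paragraph, NNAL, 1-HOP and CO "will be compared between the baseline and 9-week assessments via paired t-test", and CO also gets a mixed model. Cotinine is in neither. Its purpose is given in one direction only: "We will also evaluate toxicity by analyzing cotinine level to assure that the adverse effect of increased cotinine" (the sentence is incomplete in the text). The method is: "we will compute the number of participants with an increase in cotinine over the course of the study and consider this an adverse event". Precision is described as: "With 40 participants, confidence intervals around this adverse event percentage will be at most 0.32 percentage points". A table then gives the chance of seeing at least one rise at true rates from 0.5% to 10%.

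The plan gives no mean change in cotinine, no interval for that change, no minimum size for a rise and no reference value for the percentage. It does not say which visits define the course of the study. Urine is collected at baseline, week 3 and week 9, and cotinine concentration is among the planned assays.

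**The concern.** The protocol states an expectation about the level of cotinine in the group, but the analysis addresses a different quantity: how many individuals went up by any amount. That number does not estimate how far cotinine moved. With no reference value, a reader cannot tell whether a given count means stability, a rise or a fall.

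This matters for interpretation. The trial is single-arm and asks participants to substitute one nicotine product for another. Whether nicotine intake held, rose or fell is useful context for any change in NNAL and CO, and for planning the larger randomized trial. As written, a group whose intake had dropped could be reported only as having a number of cotinine adverse events.

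**Working it through.** **1. The plan's own figures.** The chance of at least one rise among 40 is 1 − (1 − p)^40. For p = 0.5%, 1%, 2%, 5% and 10% this gives 0.182, 0.331, 0.554, 0.871 and 0.985. These match the stated 0.18, 0.33, 0.55, 0.87 and 0.99. The exact 95% interval at 20 of 40 runs from 0.338 to 0.662, a width of 0.324. The stated 0.32 is therefore right as a proportion, and should read 32 percentage points. (The 95% level is taken from the substitution paragraph; the cotinine sentence gives none.)

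**2. What the count shows if cotinine is stable.** No minimum rise is set. With symmetric within-person variation, P(rise) = 0.5, so 40 × 0.5 = 20 rises are expected (central 95% range 14 to 26). The chance of at least one is essentially 1. The tabulated rates of 0.5% to 10% are far from this.

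**3. What the count shows if cotinine falls.** Assumptions, not in the documents: the geometric mean falls by 25%, log changes are normal, and their SD is 0.5 to 0.8. Then P(rise) = Φ(ln 0.75 / SD), with ln 0.75 = −0.288.

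| SD of log change | Standardised fall | P(rise) | Expected rises of 40 |
|---|---|---|---|
| 0.5 | 0.575 | 0.283 | 11.3 |
| 0.8 | 0.360 | 0.360 | 14.4 |

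The chance of at least one rise exceeds 0.9999 in both rows. Seeing at least one therefore does not separate stability from a fall.

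**4. Count against paired change, for the same fall.**
- Paired t-test on log cotinine, n = 40, two-sided 0.05, noncentrality (standardised fall) × √40: power 94% at SD 0.5 and 60% at SD 0.8.
- Exact 95% interval on the share of risers lying wholly below 50%: this needs 13 or fewer rises (13 of 40 has upper limit 49.1%; 14 of 40 has 51.7%). The probability is 78% at SD 0.5 and 39% at SD 0.8. The 50% reference is supplied here; the plan does not state one.

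**5. Precision of the proposed estimate.** The two-sided 95% interval for the ratio extends by a factor of exp(2.023 × SD/√40) either side: 1.17 at SD 0.5 and 1.29 at SD 0.8.

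**6. Could stability be shown?** Take 0.70 to 1.43 as an illustrative margin, with two one-sided 5% tests and no true change. The interval lies inside it in 99% of trials at SD 0.5 and 74% at SD 0.8 with 40 evaluable. At SD 0.8 with 32 evaluable (assumed), this drops to 59%. With a margin of 0.80 to 1.25 and 40 evaluable, the figures are 74% and 10%.

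**The case against.** Several points on the other side stand.

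- **Cotinine is not a hypothesis.** H2 does not include it. The no-change statement is an expectation resting on background about titration, in a 40-person feasibility pilot. A formal equivalence test is not required by anything the plan sets out to prove, and no margin has support in the documents.
- **The count suits its stated purpose.** It is there to watch for an unwanted increase. The gap is a missing estimate.
- **The count is not blind to a fall.** At 11 of 40 the exact 95% interval is 15% to 44%, which excludes one half (sign-test p = 0.006). At 14 of 40 it is 21% to 52%, which does not. It is inefficient, and it needs a reference value that the plan omits.

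A reader might infer that, without a cotinine estimate, a fall in NNAL or CO could not be read as product switching. The documents do not support that. Switching is also addressed by the parallel process growth model, the Timeline Follow-Back record of both products, the check of returned devices, and urine propylene glycol.

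A reader might also infer that a fall in cotinine would rule out replacement. It would not. The Study Design section lets participants move to stronger or weaker liquid by preference, so someone could switch fully and still show lower cotinine. With no control arm, a cotinine ratio would not settle attribution either.

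**Conclusion.** The mismatch is real but moderate in size. The protocol expects no change in cotinine, and its only cotinine analysis estimates no change and sets no benchmark. About 20 of 40 rises would be expected under stability, and about 11 to 14 under a 25% fall. In detecting that fall the paired analysis gains roughly 16 percentage points at SD 0.5 (94% against 78%) and 21 at SD 0.8 (60% against 39%).

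These figures rest on an assumed 25% fall, an assumed log-change SD of 0.5 to 0.8, normal log changes and 40 evaluable pairs. The absence of any estimate of change does not depend on them.

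The gap affects how the results can be interpreted. It invalidates no confirmatory test, and the tabulated probabilities are correct.

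**What to change.** In the Toxicity Assessment paragraph:

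1. Add urine cotinine to the baseline-to-week-9 paired analysis. Report the geometric mean ratio (log scale) with a two-sided confidence interval, using the same creatinine correction as NNAL.
2. Present it beside the NNAL and CO changes and the e-cigarette use data.
3. State that a non-significant change is not evidence of no change. If the sponsor wishes to claim that nicotine intake was maintained, a margin must be justified and fixed before data are seen; otherwise the estimate stays descriptive.
4. If the count of rises is kept, say which visits it uses, and note that about half of participants would show some rise under stability. Correct the unit of the stated interval width.

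The cost is a few lines of text and one extra summary on assays already planned, with no new visits or samples. The downside is that if variability is high, the interval may be too wide to show stability.

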## STUDY OVERVIEW

This pilot study will test the appeal and toxicity of e-cigarettes as a substitute for cigarettes among smokers with aerodigestive tract cancers or bladder cancer. Participants will receive e- cigarettes for 9 weeks and be asked to substitute the e-cigarette product for their usual combustible product. Primary outcomes include e-cigarette appeal, e-cigarette use/satisfaction and combustible tobacco toxicity.

## STUDY DESIGN CONSIDERATIONS

### INTRODUCTION

Smoking is responsible for \$130 billion in direct healthcare expenditures and half a million deaths every year in the United States, primarily from cancers, cardiovascular disease and chronic lung disease. The most recent Surgeon General report added new causal associations between active smoking and age-related macular degeneration, diabetes, colorectal cancer, liver cancer, adverse health outcomes in cancer patients and survivors, tuberculosis, erectile dysfunction, orofacial clefts in infants, ectopic pregnancy, rheumatoid arthritis, inflammation, and impaired immune function. Of all the preventable causes of disease, smoking ranks by far as the most important single modifiable risk factor because it remains a prevalent behavior (affecting about 20% of the population), because of its strong relation to many disease outcomes, and because of its lack of specificity: Smoking is linked with almost every important chronic disease.

### SMOKING AS A CAUSE OF CANCER

[figure not shown]
Among all modifiable risk factors for cancer, cigarette smoking exerts the greatest single effect, being responsible for about one-third of cancer deaths. With respect to cancer, cigarettes deliver dozens of toxins to the lung in the tar component of smoke, where they are absorbed into the surrounding tissues and transmitted to other tissues through the blood stream. Figure 1 illustrates the known mechanisms that relate continued exposure to these toxins and the onset and development of cancers. Tobacco smoke contains more than 7,000 chemicals, and at least 69 of these can cause cancer. These carcinogenic compounds deposit in the lung tissues and act locally, and are transmitted through the circulatory system to tissues remote from the lung.

For example, N-nitrosodimethylamine, and 4-aminobiphenyl are liver metabolites implicated in the association between smoking and cancer of the liver. Other metabolites, e.g. urinary 4- (methylnitrosamino)-1-(3-pyridyl)-1-butanol (NNAL), N'-nitrosonornicotine (NNN), and their glucuronide metabolites of the tobacco-specific nitrosamine (TSNA), nicotine-derived nitrosamine ketone (NNK), are subsequently concentrated in the kidney, leading to high organ exposure in those tissues and the bladder.

Some constituents (or metabolites) of tobacco smoke bind to cellular receptors and

activate protein kinases and growth receptors, which can induce inflammation, resulting in enhanced pneumocyte proliferation, activation of nuclear factor-kappa B (NF- $\kappa$ B), and tumor promotion. These same mechanisms could affect tumor growth rates after diagnosis and risk of secondary recurrence after successful treatment of the primary tumor.

**Figure 1** Pathway for causation of cancer by carcinogens in tobacco smoke

The main addictive component in tobacco, nicotine, has little toxicity in cigarette doses, especially to smokers, who are tolerant to its effects on the brain and other systems. Nicotine is also available from various nicotine replacement products that have been found to reduce cigarette consumption when given to active smokers.

Reviews of studies have found that this approach does not reduce the chances that a smoker will quit smoking. Moreover, smoker titrate their nicotine intake when given multiple nicotine products, such that urine cotinine levels remain the same when smokers are given a nicotine replacement product. More recent unpublished data show that introduction of e-cigarettes in smokers does not result in rises in saliva cotinine, but is associated with changes in cigarette consumption.

## SMOKING AMONG CANCER PATIENTS

Given the prominent role smoking plays in carcinogenesis, it is not surprising that smoking is more common in cancer patients than in the general population. In a cohort of 5185 recently diagnosed cancer patients at Roswell Park Cancer Center, 62% of all patients had some involvement with tobacco during their lives: current smokers (18%), recent quitters (10%), or former smokers (35%). Cancers with the highest rates of current

[figure not shown]
smoking included head & neck (29%), bladder (27%) and lung (24%). Another study summarized cross-sectional and longitudinal studies of smoking after cancer diagnosis among lung and head & neck cancer patients, and found an overall rate of 33%. Summary of the longitudinal studies in this review found little evidence to support the notion that cancer patients who smoke tend to quit over time. There were few studies of level of addiction among cancer patients that some, but given their life circumstances and the lack of evidence for quitting, it would be reasonable to conclude that these individuals are heavily addicted smokers that would be expected to be relatively refractory to treatment and for whom alternatives to cessation should be considered.

## OUTCOMES FOR SMOKING-RELATED CANCERS IN SMOKERS VS. FORMER SMOKERS

### EFFECT ON MORTALITY

In the Roswell Park study investigators assessed smoking status for 5185 cancer patients enrolled into treatment programs between 1982 and 1998. Survival curves like the one in Figure 2 compared survival by disease site for current vs former smokers/recent quitters. Not all the curves are as striking as this one, which shows overall survival for head & neck cancer, but continued smoking was an important risk factor for many cancers and overall, with adjusted hazard ratio for time to mortality being 1.29 (95% CI 1.17, 1.42) for current vs. former smokers and 1.18 (1.04, 1.33) for current vs. recent quitters after adjusting for grade and stage, age, BMI, and several other risk factors. Given that many of the recent quitters would have relapsed (see below), the increased survival in recent quitters represents a possible harm reduction influence conferred by decreased daily cigarette consumption. Furthermore, a systematic review of observational studies examining the influence of smoking cessation after diagnosis of early stage lung cancer suggested that the mortality benefit seen with smoking cessation was due more to reduced cancer progression rather than fewer cardiorespiratory deaths.

Figure 2. Overall survival: head & neck cancer, men, adjusted for age and stage

From Warren, et al.

### EFFECT ON RISK FOR SECOND PRIMARY CANCER

Other studies have looked specifically at how smoking status relates to the probability of developing a second primary. A study of over 1484 patients with a primary non-small cell lung carcinoma (median follow-up 26 months) found that 66 developed a second primary lung cancer (SPLC). Among smokers the only variable associated with SPLC development was smoking pack-years (entered as a continuous variable), with hazard ratios indicating an 8% increase in risk for SPLC development for each additional 10 pack-years. A much larger prospective study pooled data from five prospective cohorts, examining hazard of developing second primary cancers and compared never-smokers with former smokers <20 cigarettes per day, former smoker > 20 cigarettes per day, current smoker < 20 cigarettes per day, and current smoker ≥ 20 cigarettes per day. Table 1, adapted from the study, shows hazard ratios for second cancer development for lung, bladder, kidney, and head/neck cancers. Compared to never smokers, higher levels of former and current smoking showed substantially greater hazard of second primary cancers in all categories, with current smokers having higher risk compared to former smokers. Note the finding of a dose-response among smokers, showing consistently higher hazard ratios for those who smoked ≥ 20 cigarettes per day vs. those who smoked less. This adds justification to the idea that e-cigarette substitution could improve cancer outcomes even if the smoker was not able to achieve complete substitution of the e-cigarette product.

Table 1. Association between smoking status and cigarettes smoked per day and risk of a second primary smoking-associated cancer among survivors of lung, bladder, and head & neck cancers. Adapted from Shiels, et al.

Smoking Status	Stage I Lung Cancer				Bladder Cancer				Head/Neck Cancer			
	Second Cancer		HR	95% CI	Second Cancer		HR	95% CI	Second Cancer		HR	95% CI
	No	Yes			No	Yes			No	Yes		
Never	186	3	1.0	Referent	1,080	28	1.0	Referent	542	18	1.0	Referent
Former												
< 20 cig/d	419	6	0.90	0.22 to 3.68	1,523	78	1.84	1.19 to 2.85	511	32	1.60	0.87 to 2.8
≥ 20 cig/d*	674	19	1.69	0.48 to 5.94	1,793	106	2.12	1.38 to 3.26	567	66	2.97	1.74 to 5.0
Current												
< 20 cig/d	482	18	2.58	0.74 to 8.98	623	49	2.81	1.76 to 4.50	408	42	2.89	1.64 to 5.0
≥ 20 cig/d*	389	17	3.26	0.92 to 11.6	448	41	3.67	2.25 to 5.99	345	51	4.45	2.56 to 7.7
P trend†	.002				< .001				< .001			

Adjusted for age, sex, race, education, BMI, cohort, time from baseline to first cancer, and follow-up time.

